## 5.2 Outcome definitions

The following serious adverse events will be collected as secondary outcomes and are expected to occur during this study, and will not require additional reporting as SAEs (see section 7 below). Where possible, definitions are aligned with the ARC-2 consensus document.

Outcome	Endpoint definition
Death	
Death from all-causes can be defined as one of the following classifications:
 
 
Cardiovascular death Defined as any death resulting from cardiovascular causes. This may include death caused by: 
 
a. Acute MI
 
b. Sudden cardiac, including unwitnessed death
 
c. Heart Failure
 
d. Stroke
 
e. Cardiovascular procedures
 
f. Cardiovascular haemorrhage
 
g. Other cardiovascular cause
 
 
 
Non-cardiovascular death Defined as any death not thought to be the result of a cardiovascular cause. This may include death caused by: 
 
a. Malignancy
 
b. Pulmonary causes
 
c. Infection (including sepsis)
 
d. Gastrointestinal causes
 
e. Accident or trauma
 
f. Other non-cardiovascular organ failure
 
g. Other non-cardiovascular cause
 
 
 
Undetermined Defined as death not classified under any other category because of the absence of any relevant source documents. For endpoint determination these deaths will be classified as cardiovascular.
 

Myocardial infarction	
Myocardial infarction will be defined according to the ARC-2 definition below.
 
 
Spontaneous myocardial infarction (prior to or ≥48 hours after PCI/CABG)  Detection of a rise and/or fall of cardiac troponin I or T, with at least one value higher than the 99th percentile upper reference limit (URL) AND symptoms consistent with ischaemia OR dynamic electrocardiogram (ECG) changes (including ≥1mm ST elevation or ST depression, new left bundle branch block (LBBB) or >3mm T-wave
 

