Bleeding	
Bleeding will be defined using the Bleeding Academic Research Consortium (BARC) 3 criteria as below:
 
Type 0: No bleeding
 
Type 1
 
 
Bleeding that is not actionable and does not cause the patient to seek unscheduled performance of studies, hospitalization, or treatment by a healthcare professional; may include episodes leading to self-discontinuation of medical therapy by the patient without consulting a healthcare professional
 
 
Type 2
 
 
Any overt, actionable sign of haemorrhage (e.g. more bleeding than would be expected for a clinical circumstance, including bleeding found by imaging alone) that does not fit the criteria for type 3, 4, or 5 but does meet at least one of the following criteria: (1) requiring nonsurgical, medical intervention by a healthcare professional, (2) leading to hospitalization or increased level of care, or (3) prompting evaluation
 
 
Type 3
 
 
Type 3a
 

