	
 
○ Overt bleeding plus haemoglobin drop of 3 to <5 g/L* (provided haemoglobin drop is related to bleed)
 
○ Any transfusion with overt bleeding
 
• Type 3b 
 
○ Overt bleeding plus haemoglobin drop <math>\geq 5</math> g/dL* (provided haemoglobin drop is related to bleed)
 
○ Cardiac tamponade
 
○ Bleeding requiring surgical intervention for control (excluding dental/nasal/skin/haemorrhoid)
 
○ Bleeding requiring intravenous vasoactive agents
 
 
 
• Type 3c 
 
○ Intracranial haemorrhage (does not include microbleeds or haemorrhagic transformation, does include intraspinal)
 
○ Subcategories confirmed by autopsy or imaging or lumbar puncture
 
○ Intraocular bleed compromising vision
 
 
 
 
Type 4: CABG-related bleeding
 
 
• Perioperative intracranial bleeding within 48 hours
 
• Reoperation after closure of sternotomy for the purpose of controlling bleeding
 
• Transfusion of <math>\geq 5</math> units whole blood or packed red blood cells within a 48-hour period
 
• Chest tube output <math>\geq 2</math>L within a 24-hour period
 
 
Type 5: fatal bleeding
 
 
• Type 5a 
 
○ Probable fatal bleeding; no autopsy or imaging confirmation but clinically suspicious
 
 
 
• Type 5b 
 
○ Definite fatal bleeding; overt bleeding or autopsy or imaging confirmation
 
 
 

Vascular complication	
Vascular complications will be defined according to the Valve Academic Research Consortium 2 (VARC-2) criteria as below:
 
Major complication
 
 
• Aortic dissection or aortic rupture, annulus rupture, left ventricle perforation, or new apical aneurysm/pseudo-aneurysm OR
 
• Access site or access-related vascular injury (dissection, stenosis, perforation, rupture, arterio-venous fistula, pseudoaneurysm, haematoma, irreversible nerve injury, compartment syndrome, percutaneous closure device failure) leading to death, life-threatening or major (VARC) bleeding, visceral ischaemia, or neurologic impairment OR
 

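### The type 3a haemoglobin band is in g/L and the type 3b band in g/dL, so a bleed with a larger drop can be graded below one with a trivial drop

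*Protocol*

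**What the plan says.** The bleeding row of the outcome table in Protocol section 5.2 opens: "Bleeding will be defined using the Bleeding Academic Research Consortium (BARC) 3 criteria as below". Within type 3, the parts that matter here are:

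- **Type 3a, haemoglobin route:** "Overt bleeding plus haemoglobin drop of 3 to" less than "5 g/L* (provided haemoglobin drop is related to bleed").
- **Type 3a, other route:** "Any transfusion with overt bleeding", with no haemoglobin threshold.
- **Type 3b, haemoglobin route:** overt bleeding with a drop of at least 5 "g/dL* (provided haemoglobin drop is related to bleed"). Tamponade, surgical control of the bleed and intravenous vasoactive agents are separate routes into 3b.
- **Type 3c:** intracranial bleeding, and intraocular bleeding that compromises vision.

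Type 2 takes overt, actionable bleeding "that does not fit the criteria for type 3, 4, or 5 but does meet at least one of the following criteria": non-surgical treatment by a professional, hospitalisation or more intensive care, or a prompted evaluation.

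On the status of these events, section 5.2 states: "The following serious adverse events will be collected as secondary outcomes and are expected to occur during this study". It adds that they need no further SAE report.

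**The concern.** Types 3a and 3b are successive grades of one scale, and their haemoglobin criteria share the boundary figure 5. That works only if both are in the same unit. Here the lower grade is in g/L and the higher in g/dL, so the scale has a hole in the middle and its lower band sits at a tenth of the size that the upper band implies.

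What is at stake is the severity grading of a harm. Events in the section 5.2 table are exempt from additional SAE reporting, and section 9.1 reserves SAE and NSAE reports for unexpected events not defined as outcomes. The grade assigned under section 5.2 is therefore the main record of how serious a bleed was. Bleeding is also a harm on which the arms could plausibly differ: under section 6.6 the PCI arm takes clopidogrel, and the placebo-procedure arm takes a matching placebo, for up to 6 months.

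**Working it through.** The protocol states no derived figure to reproduce. The check is a unit conversion followed by a classification of example drops.

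**Inputs (all from section 5.2, bleeding row)**
- Type 3a: drop of 3 to <5, unit g/L.
- Type 3b: drop of ≥5, unit g/dL.
- Conversion: 1 g/dL = 10 g/L.

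**Step 1: put both bands on one scale**
- Type 3a = 3 to <5 g/L, or 3/10 to <5/10 = 0.3 to <0.5 g/dL.
- Type 3b = ≥5 × 10 = ≥50 g/L.

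**Step 2: find the gap**
- The upper end of 3a is 5 g/L and the lower end of 3b is 50 g/L.
- Drops of 5 to <50 g/L (0.5 to <5 g/dL) lie in neither band. The width is 50 − 5 = 45 g/L.

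**Step 3: classify overt bleeds by haemoglobin drop alone**

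| Related drop (g/L) | As written | Both bands in g/dL | Both bands in g/L |
|---|---|---|---|
| 3 | 3a | none | 3a |
| 4 | 3a | none | 3a |
| 5 | none | none | 3b |
| 10 | none | none | 3b |
| 30 | none | 3a | 3b |
| 40 | none | 3a | 3b |
| 49 | none | 3a | 3b |
| 50 | 3b | 3b | 3b |

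Here, none means that neither haemoglobin criterion is met. The bleed may still be type 3 by another route, or type 2.

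**Step 4: read the result**
- Either common unit removes the gap. The text as written matches neither consistent scale.
- As written the grading is not monotone: an overt bleed with a 4 g/L drop is 3a, while one with a 40 g/L drop and no other type 3 feature is at most type 2.
- If the type 3b unit is applied to the type 3a numbers, the band is 30 to <50 g/L. All of it lies inside the 5 to <50 g/L gap, so the present text captures none of that band through haemoglobin.

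**Step 5: choose between the two consistent readings**
- With both bands in g/L, any related drop of 5 g/L or more would share a grade with tamponade and with bleeding that needs surgery.
- With both in g/dL, the type 3b line stands as printed and only the type 3a unit changes. That is the more coherent reading of the section, and the sponsor can confirm it against the BARC criteria that the section cites.

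**The case against.** The best case on the other side accepts the mismatch and disputes its consequences. Most of that case is right.

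- **Bleeds in the gap are misgraded, not lost.** A bleed with a 40 g/L drop is still type 3 if there was a transfusion, tamponade, surgical control, vasoactive agents, or an intracranial or sight-threatening intraocular bleed. Otherwise it is type 2 if actionable. It remains a bleeding event whatever its type. This stands.
- **Over-grading is limited.** The 3a line needs overt bleeding and a drop related to it, so a small laboratory change alone never qualifies. Section 6.12 schedules a full blood count at baseline only, so later values would come mainly from clinically driven tests. This stands too.
- **An assessor who knows the scale may spot the slip.** Possibly, but the protocol should not depend on that. The haemoglobin exclusion criterion in section 5.6 is in g/L, so the unit will not look foreign at a site, and section 15.1 plans no routine monitoring visits.

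A reader might also infer three stronger things that the document does not support:

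- **That major bleeding is misclassified.** The protocol never calls BARC type 3 major. It uses that word for bleeding only in the VARC terms under vascular complications.
- **That bleeding is a leading harm outcome.** It is one of several events in section 5.2. It is not named among the outcome measures in section 5.1 or the analyses in section 16.
- **That the error could create a difference between arms.** The same text applies to both arms, and section 6.8.1 gives the discharge and follow-up forms to blinded staff. All participants also receive an aspirin and clopidogrel load (section 6.5.2) and aspirin afterwards (section 6.5.6). Misgrading of this kind may blur a true difference, but nothing in the document shows how it would produce a false one.

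**Conclusion.** The point holds as an error in an outcome definition. As written, the type 3a and 3b haemoglobin bands are separated by 45 g/L, the whole 30 to <50 g/L range falls in that gap, and a bleed with a larger drop can be graded below one with a drop of 3 to <5 g/L. No other section corrects it.

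Its reach is narrow: the severity grade of bleeds that enter type 3 on haemoglobin alone. The number of such bleeds cannot be estimated, because the protocol gives no bleeding rate. The primary outcome, the sample size, the two key secondary outcomes and the win-ratio hierarchy do not depend on it.

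The conclusion rests on two assumptions: that the protocol itself prints g/L in the 3a line, and that the bands were meant to be adjacent. The first is likely, since g/dL is intact a few lines below. The second follows from the shared boundary at 5. The error should be corrected because a literal reader will misgrade bleeds and the remedy is almost free.

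**What to change.** In section 5.2, state both haemoglobin criteria in one unit so that the bands meet, and give the equivalent in the other unit:

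- Type 3a: overt bleeding with a related drop of 3 to <5 g/dL (30 to <50 g/L).
- Type 3b: overt bleeding with a related drop of ≥5 g/dL (≥50 g/L).

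This keeps the type 3b line as it is and follows the BARC scale that the section says it uses. Grade all bleeds by the corrected text, and regrade any already classified on haemoglobin under the current wording.

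The cost is a one-line correction at the next amendment and a notice to sites. No change to the design, the sample size or the analysis is needed. Left until the data are in, the same correction would mean going back to the haemoglobin values of bleeds already graded.

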### 5.3 Trial flowchart

## 5.4 Participating Trial Sites

Participants will be recruited at NHS hospital trusts within the United Kingdom based on site suitability as assessed by the study team. A current list of recruiting sites can be found on the trial website (<http://www.lshtm.ac.uk/REPRIEVED>). Participants will be identified in the course of their clinical care at these participating sites. Potential participants will also be able to self-refer for involvement in the trial.

It is anticipated that >100 patients per site per year will meet inclusion criteria and be considered for the study; it is recognised that there is underdiagnosis of both HFpEF and coronary artery disease, and attempts will be made at each site to increase detection of coronary artery disease in patients diagnosed with HFpEF and vice versa.

## 5.5 Participant inclusion criteria

1. A diagnosis of HFpEF, defined by the European Society of Cardiology (ESC) criteria, as:
  - a. Symptoms of heart failure (New York Heart Association (NYHA) class II-IV) **and**
  - b. Left ventricular ejection fraction  $\geq 50\%$  **and**
  - c. NT-pro-BNP  $> 125$  pg/ml in sinus rhythm or  $> 365$  pg/ml in atrial fibrillation **and**
  - d. One or more of the following objective signs of left ventricular diastolic dysfunction:
    - i. Invasively measured left ventricular end diastolic pressure  $\geq 15$  mmHg at rest or  $\geq 25$  mmHg on exercise (directly measured or estimated via pulmonary capillary wedge pressure)
    - ii. Estimated pulmonary artery systolic pressure  $> 35$  mmHg or tricuspid regurgitation velocity  $> 2.8$  m/s on echocardiography
    - iii. Left atrial volume index  $> 34$  ml/m^2 in patient in sinus rhythm or left atrial volume index  $> 40$  ml/m^2 in atrial fibrillation
    - iv. Relative left ventricular wall thickness  $> 0.42$
    - v. Left ventricular mass index  $\geq 95$  g/m^2 in females or  $\geq 115$  g/m^2 in males
    - vi. Mitral E/E' ratio  $> 9$

**plus**
2. Significant coronary artery disease defined as:
  - a. Functionally significant disease in at least one major proximal epicardial coronary artery (British Cardiovascular Intervention Society Jeopardy Score  $\geq 4$ ) which is suitable for PCI and has a fractional flow reserve (FFR)  $\leq 0.80$  measured with FFR, non-hyperaemic pressure ratio (NHPR)  $\leq 0.89$ , or estimated with computational fluid dynamics during invasive angiography (e.g. VFR) or CT-FFR.

Assessments of left ventricular ejection fraction and coronary anatomy must have been performed within 12 months prior to enrolment.

## 5.6 Participant exclusion criteria

Exclusion criteria are:

1. Age  $< 18$  years
2. People without capacity to provide informed consent

3. PCI contraindicated or not feasible on coronary angiography or screening CTCA
4. Contraindication to clopidogrel/dual antiplatelet therapy
5. Recent acute myocardial infarction or coronary revascularisation (within 90 days)
6. Enrolment in another interventional study which may affect study outcomes
7. Severe chronic obstructive pulmonary disease (GOLD stage  $\geq 3$ )
8. Haemoglobin  $\leq 80$  g/L
9. Other cardiac diagnosis as a cause for HFpEF (hypertrophic cardiomyopathy, untreated severe left sided valvular disease, cardiac amyloidosis)

Eligibility will be determined by the investigators at the recruiting site.

### **5.6.1 Angina**

Angina is not an exclusion criterion, as patients with HFpEF may experience ischaemia as breathlessness, angina, fatigue or effort intolerance, or a combination of these symptoms, all of which may impair quality of life and all of which may be modified by PCI. There is also no specific evidence of the effectiveness of PCI at relieving angina in HFpEF, where the mechanisms driving symptoms differ substantially from patients without heart failure. Finally, specific clinician attributed terms often fail to adequately capture the complexity of symptoms and lived experience of patients with HFpEF.

However, where angina is the sole symptom, participants would not be eligible for inclusion as they would not meet the inclusion criteria for Symptoms of Heart Failure, as angina is not a direct symptom of the condition.

## **6 STUDY PROCEDURES**

### **6.1 Screening**

#### **6.1.1 Patient population for screening**

All patients who have a potential diagnosis of HFpEF and coronary artery disease should be screened for eligibility.

#### **6.1.2 Initial approach to patients**

The initial approach to potential trial participants must be performed by members of the direct care team. A member of the direct care team must obtain verbal agreement from the patient before the research team contacts the patient and accesses their data for screening.

#### **6.1.3 Sources of potential participants**

It is recommended to screen from the following sources:

- Patients referred to the Heart Team for consideration of revascularisation or heart failure optimisation
- Patients seen in outpatient clinics for the assessment or management of coronary artery disease
- Patients seen in outpatient clinics for the assessment or management of HFpEF
- Patients admitted to hospital who are referred for invasive or non-invasive assessment for coronary artery disease
- Patients admitted to hospital with decompensated heart failure with a new or prior diagnosis of HFpEF

#### **6.1.4 Screening CT-FFR**

Consenting potential participants who meet the diagnostic criteria for HFpEF but have not recently been investigated for coronary artery disease will undergo screening CT coronary angiography with FFR assessment (CT-FFR) to determine the presence of coronary artery disease. Patients confirmed to have significant coronary artery disease ( $\text{FFR} \leq 0.80$  in at least one main epicardial vessel) will be enrolled in the randomised trial. All potential participants attending this appointment and those enrolled in the trial will receive travel expenses and a £10 gift voucher as a token of appreciation for their participation. Feasibility of PCI will be assessed prior to randomisation from invasive angiography or novel techniques for PCI planning from CTCA to ensure the maximal number of enrolled patients are randomised.

#### **6.1.5 Screening Logs**

Full detailed screening logs of all patients screened for inclusion in the trial will be completed at sites, and will be requested periodically by the CTU. It is anticipated that during the pilot phase screening logs will be requested monthly, and afterwards will be requested every three months.

Only patients who complete the screening process (i.e. randomised, declined, met an exclusion criterion) are required to be entered.

The screening log will include anonymous demographic information in order to monitor representativeness of the patient population. Sex, age, gender and ethnicity will be collected as well as refusals due to language.

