## **6.9 Internal pilot study**

The trial will include a 12-month internal pilot phase to confirm the feasibility of REPRIEVED. Perceived major risks to recruitment are; whether the expected proportion of screened patients have significant coronary artery disease (CAD), whether participants will consent to enrolment and whether there is a risk of emergency unblinding;

	Red	Amber	Green
Number of participants recruited	<30	30-50	>50
Blinding Index	≥0.30	≤0.30	≤0.20
Proportion of screened with significant CAD (%)	≤30	30-40	≥40
Patient consent from eligible patients (%)	<30	30-50	>50
Emergency unblinding (%)	> 10	5-10	<5

Table 3 – Criteria for progression following the 12-month internal pilot study.

During the internal pilot detailed screening data will be collected to determine whether there are inclusion or exclusion criteria which are impacting recruitment. Achievement of the green criteria will lead to direct continuation of the trial unchanged. Meeting several amber criteria will lead to discussions between the Trial Management Group, Trial Steering Committee and funder to determine what protocol amendments are needed. Meeting several red criteria will lead to discussions as to whether the trial will continue and, if so, what amendments are needed.

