### **6.13 Radiology Assessments**

After consent but before randomisation, patients who have not been investigated for coronary artery disease will have a screening CT coronary angiogram to confirm their eligibility for the study. We estimate that half of these patients will not have coronary artery disease, they will exit the study and not be randomised. The other half will have coronary disease and will then be randomised.

Of the randomised population, all will have a coronary angiogram, and half will have a percutaneous coronary intervention procedure. This includes patients who have had a prior angiogram or have had a CT coronary angiogram. All procedures will be performed as per clinical standards of care and no new scanning sequences will be used.

The study does not involve radioactive substances or radiotherapy and will be reviewed via the HRA-managed radiation assurance route.

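### Section 6.1.5 does not require patients without significant coronary disease to be logged, yet the pilot criterion on CAD yield in section 6.9 needs them in its denominator

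*Protocol*

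**What the plan says.** **Protocol 6.1.5 (screening logs).** The section opens broadly: "Full detailed screening logs of all patients screened for inclusion in the trial will be completed at sites". It says the CTU expects to request the logs monthly during the pilot and every three months afterwards. It then limits what must be entered: "Only patients who complete the screening process (i.e. randomised, declined, met an exclusion criterion) are required to be entered".

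**Protocol 5.5 and 5.6 (eligibility).** Significant coronary disease is the second inclusion criterion, introduced by "Significant coronary artery disease defined as" and described as "Functionally significant disease in at least one major proximal epicardial coronary artery", with further conditions. None of the nine exclusion criteria is the absence of such disease. The nearest, number 3, concerns whether PCI is contraindicated or not feasible.

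**Protocol 6.13 (radiology).** About half of the patients sent for a screening CT coronary angiogram are expected to have no coronary disease, and "they will exit the study and not be randomised".

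**Protocol 6.9 (internal pilot).** One of the five progression criteria is "Proportion of screened with significant CAD": red at 30% or below, amber from 30% to 40%, green at 40% or above. The section names this yield as a major risk to recruitment. It adds that in the pilot "detailed screening data will be collected to determine whether there are inclusion or exclusion criteria which are impacting recruitment". It does not define the denominator or name a data source.

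**The concern.** The word *only* and the *i.e.* make the list in 6.1.5 a closed one, and failing an inclusion criterion is not on it. A patient whose screening CT shows no significant disease has finished screening, but has not been randomised, has not declined and has met no exclusion criterion. A site that follows the sentence literally may leave that patient off the log.

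This conflicts with the opening of the same section, which covers everyone screened. It also conflicts with 6.9, which needs inclusion failures recorded for two purposes: to form the denominator of the CAD criterion, and to show which inclusion criteria hold back recruitment.

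At stake is whether that criterion can be trusted in the situation it is meant to reveal, namely a yield below expectation. Entries not made during the pilot may not be recoverable afterwards.

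**Working it through.** The pilot cut-offs are set values with no formula behind them, so there is no stated figure to reproduce. The check is how far missing negatives would move the criterion.

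**Inputs**
- Cut-offs: red at or below 30%, green at or above 40% (Protocol 6.9). Values of exactly 30% and 40% each touch the amber band too; here 30% is read as red and 40% as green.
- Expected yield: about 50% among CT-screened patients (Protocol 6.13).
- *p*: true proportion of screened patients with significant disease, varied below.
- *f*: share of patients without significant disease who are logged. **Assumption:** the protocol gives no value, so the full range 0 to 1 is considered.
- **Assumption:** every patient with significant disease is logged, and the criterion is computed from the log.

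**Formulas**
- Apparent yield = p / (p + (1 − p) f).
- Setting this to at least 0.40 gives green when f ≤ 0.6p / (0.4(1 − p)).

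**Share of negatives that must be missing for a green reading**

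| True yield | Largest f that reads green | Smallest share missing |
|---|---|---|
| 30% | 0.18/0.28 = 0.643 | 35.7% |
| 25% | 0.15/0.30 = 0.500 | 50.0% |
| 20% | 0.12/0.32 = 0.375 | 62.5% |
| 15% | 0.09/0.34 = 0.265 | 73.5% |
| 50% | 0.30/0.20 = 1.5 (above 1) | none; already green |

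**Per 100 screened**
- True yield 30%: 30 positives and 70 negatives. With 25 negatives missing, 30/75 = 40%, green. With half missing, 30/(30 + 35) = 46.2%, green. With a quarter missing, 30/(30 + 52.5) = 36.4%, amber.
- True yield 20%: 20 positives and 80 negatives. With 50 missing, 20/50 = 40%, green. With half missing, 20/60 = 33.3%, amber.
- True yield 50%: with half missing, 50/75 = 66.7%. The number is too high but the colour is unchanged.

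**Limits of the range.** With f = 1 the criterion equals the true yield. With f = 0 the formula gives 100% at any true yield. That extreme would not be met exactly, because patients without significant disease who decline or meet an exclusion criterion must be logged.

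**The case against.** The strongest reply has four parts.

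1. **The bracket may be loose shorthand.** The governing phrase is completion of screening, and a CT-negative patient has completed it. The bracket may be meant only to keep patients still in work-up off the log. Even read literally, such patients are not required to be entered; they are not barred. This stands against any claim that the log omits them as a settled fact. It does not remove the contradiction, because sites must act on a closed list.

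2. **The criterion is not tied to the log.** Patients consent before the screening CT, they receive travel expenses and a voucher (6.1.4), and 6.8.1 lists a registration form and an eligibility form. CT negatives might be counted from such records. This stands, and it makes the bias conditional. But the protocol does not say they will be counted that way, and the log is the only record of all screened patients it describes. Patients ruled out on existing imaging (6.1.3 recommends screening those referred for coronary assessment) may never consent and so may have no other record.

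3. **The consequence is limited.** Under 6.9, several amber or several red criteria lead to discussions; no single criterion stops the trial. A low yield would also tend to show in the number recruited. This stands.

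4. **Some sites may log negatives under exclusion criterion 3.** That would reduce the loss, but could make it differ between sites.

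A reader might go further and infer that the criterion cannot detect a low yield, or that the demographic monitoring drawn from the log is distorted. The protocol supports neither. Detection fails only if enough negatives are missing and no other source is used. Nothing shows that patients without coronary disease belong in the comparison for representativeness, since objective 5 in section 4 concerns people with both HFpEF and coronary disease.

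**Conclusion.** The point holds as an internal contradiction with a conditional consequence. Section 6.1.5 asks for everyone screened and then does not require entry of patients who fail an inclusion criterion, while 6.9 depends on those patients.

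If the log feeds the CAD criterion, all positives are logged and some negatives are not, the criterion is biased upwards. A true yield at the top of the red band reads green once about 36% of negatives are missing; a true yield of 20% needs about 62.5% missing. At the expected yield of about 50% the number is inflated but the status is correctly green. The error therefore matters only if the yield disappoints, which is the case the criterion exists to show.

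It is worth correcting because the rule is explicit and the correction is nearly free. It does not threaten the trial's continuation by itself, and it has no bearing on the sample size or the efficacy analysis.

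**What to change.** - **Section 6.1.5:** extend the bracket to four categories: randomised; declined; did not meet an inclusion criterion (with the reason, including no significant CAD); met an exclusion criterion.
- **Section 6.9:** state the numerator, denominator and data source of the CAD criterion. One workable denominator is all patients with HFpEF who had a completed coronary assessment at screening; other choices are possible if stated.

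The cost is one phrase in 6.1.5, a short definition in 6.9 and a few more anonymous log lines per site. The change should be made before pilot screening data accumulate; if recruitment has begun, sites should be asked to add inclusion failures retrospectively where they can be traced.
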